10.7. Appendix 7: ECG Findings of Potential Clinical Concern

ECG Findings That May Qualify as AEs

Marked sinus bradycardia (rate <40 bpm) lasting minutes.New PR interval prolongation >280 msec.New prolongation of QTcF to >480 msec (absolute) or by \geq60 msec from baseline.New-onset atrial flutter or fibrillation, with controlled ventricular response rate: ie, rate <120 bpm.New-onset type I second-degree (Wenckebach) AV block of >30 seconds' duration.Frequent PVCs, triplets, or short intervals (<30 seconds) of consecutive ventricular complexes.
ECG Findings That May Qualify as SAEs

QTcF prolongation >500 msec.New ST-T changes suggestive of myocardial ischemia.New-onset left bundle branch block (QRS >120 msec).New-onset right bundle branch block (QRS >120 msec).Symptomatic bradycardia.Asystole:
In awake, symptom-free participants in sinus rhythm, with documented periods of asystole \geq3.0 seconds or any escape rate <40 bpm, or with an escape rhythm that is below the AV node.In awake, symptom-free participants with atrial fibrillation and bradycardia with 1 or more pauses of at least 5 seconds or longer.Atrial flutter or fibrillation, with rapid ventricular response rate: rapid = rate >120 bpm.Sustained supraventricular tachycardia (rate >120 bpm) ("sustained" = short duration with relevant symptoms or lasting >1 minute).

- Ventricular rhythms >30 seconds' duration, including idioventricular rhythm (heart rate <40 bpm), accelerated idioventricular rhythm (HR >40 bpm to <100 bpm), and monomorphic/polymorphic ventricular tachycardia (HR >100 bpm (such as torsades de pointes)).
- Type II second-degree (Mobitz II) AV block.
- Complete (third-degree) heart block.

ECG Findings That Qualify as SAEs

- Change in pattern suggestive of new myocardial infarction.
- Sustained ventricular tachyarrhythmias (>30 seconds' duration).
- Second- or third-degree AV block requiring pacemaker placement.
- Asystolic pauses requiring pacemaker placement.
- Atrial flutter or fibrillation with rapid ventricular response requiring cardioversion.
- Ventricular fibrillation/flutter.
- At the discretion of the investigator, any arrhythmia classified as an adverse experience.

The enumerated list of major events of potential clinical concern are recommended as “alerts” or notifications from the core ECG laboratory to the investigator and Pfizer study team, and not to be considered as all inclusive of what to be reported as AEs/SAEs.

10.8. Appendix 8: Abbreviations

The following is a list of abbreviations that may be used in the protocol.

Abbreviation	Term
Abl	Abelson
abs	absolute
ADL	activity of daily living
AE	adverse event
ALT	alanine aminotransferase
AP	accelerated phase
AST	aspartate aminotransferase
AUC	area under the concentration-time curve
AUC _{inf}	area under the plasma concentration-time curve from time zero extrapolated to infinite time
AUC _{last}	area under the plasma concentration-time profile from time zero to the time of the last quantifiable concentration
AV	atrioventricular
BBS	Biospecimen Banking System
BMI	body mass index
BP	blood pressure
bpm	beats per minute
BSA	body surface area
BUN	blood urea nitrogen
CFR	Code of Federal Regulations
CI	confidence interval
CIOMS	Council for International Organizations of Medical Sciences
CK	creatine kinase
CKD-EPI	Chronic Kidney Disease Epidemiology Collaboration
C _{last}	last quantifiable concentration
C _{last*}	predicted plasma concentration at the last quantifiable time point estimated from the log-linear regression analysis
CL/F	apparent clearance after oral dose
C _{max}	maximum plasma concentration
CML	chronic myeloid leukemia
CO ₂	carbon dioxide
COVID-19	coronavirus disease 2019
CP	chronic phase
CRF	case report form
CRO	contract research organization
CRU	clinical research unit
CSR	Clinical Study Report
CT	clinical trial

Abbreviation	Term
CTMS	clinical trial management system
DCT	data collection tool
DILI	drug-induced liver injury
DMC	Data Monitoring Committee
DNA	deoxyribonucleic acid
EC	ethics committee
ECC	Emergency Contact Card
ECG	electrocardiogram
EDB	exposure during breastfeeding
eCRF	electronic case report form
eGFR	estimated glomerular filtration rate
EDP	exposure during pregnancy
EMA	European Medicines Agency
EU	European Union
EudraCT	European Clinical Trials Database
FSH	follicle-stimulating hormone
GCP	Good Clinical Practice
GGT	gamma-glutamyl transferase
GI	gastrointestinal
HBcAb	hepatitis B core antibody
HBsAb	hepatitis B surface antibody
HBsAg	hepatitis B surface antigen
HCVAb	hepatitis C antibody
HIV	human immunodeficiency virus
HR	heart rate
HRT	hormone replacement therapy
IB	Investigator's Brochure
ICD	informed consent document
ICH	International Council for Harmonisation
ID	Identification
IND	Investigational New Drug
INR	international normalized ratio
IP	investigational product
IPAL	Investigational Product Accountability Log
IRB	Institutional Review Board
IV	intravenous
k_{el}	terminal phase rate constant
LBBB	left bundle branch block
LFT	liver function test
MCH	mean corpuscular hemoglobin
MCHC	mean corpuscular hemoglobin concentration

Abbreviation	Term
MCV	mean corpuscular volume
msec	millisecond
N/A	not applicable
PCR	polymerase chain reaction
Ph+	Philadelphia chromosome positive
PIP	Pediatric Investigation Plan (EU)
PK	pharmacokinetic(s)
PR interval	time from the beginning of the P wave to the beginning of QRS complex
PT	prothrombin time
PVC	premature ventricular contraction
QRS	time from ECG Q wave to the end of the S wave corresponding to ventricle depolarization
QT	time from the beginning of the QRS complex to the end of the T wave
QTc	corrected QT interval
QTcF	QTc corrected using Fridericia's formula
qual	qualitative
RBC	red blood cell
RNA	ribonucleic acid
SAE	serious adverse event
SAP	Statistical Analysis Plan
SARS-CoV-2	severe acute respiratory syndrome coronavirus 2
SCr	serum creatinine
SoA	schedule of activities
SOP	standard operating procedure
Src	sarcoma
SRSD	single-reference safety document
SUSAR	Suspected Unexpected Serious Adverse Reaction
t _½	terminal elimination half-life
TBili	total bilirubin
TEAE	treatment-emergent adverse event
THC	tetrahydrocannabinol
T _{max}	time for C _{max}
TKI	tyrosine kinase inhibitor
ULN	upper limit of normal
US	United States
V _z /F	apparent volume of distribution after oral dose
WBC	white blood cell
WOCBP	woman of childbearing potential

1. AMENDMENTS FROM PREVIOUS VERSION(S)

None.

2. INTRODUCTION

Bosutinib (PF-05208763, Bosulif®) is an orally active Src/Abl kinase inhibitor indicated for the treatment of adult patients with Ph+ CML.

The purpose of this study is to support the bridging of current clinical 25 mg capsule and proposed commercial 100 mg capsule in healthy participants under fed condition and to evaluate the effect of food on bosutinib plasma pharmacokinetics following administration of the proposed commercial 100 mg capsule strength. The relative bioavailability study will be conducted in the fed state since bosutinib is currently labeled to be administered with food.

2.1. Study Design

This is a Phase 1, randomized, open-label, 3-period, 4-sequence, crossover, single-dose study in approximately 28 healthy participants (7 participants per sequence). Participants will be randomized to 1 of the 4 sequences of treatment described in Table 1.

Note: “Enrolled” means a participant’s agreement to participate in a clinical study following completion of the informed consent process and screening. A participant will be considered enrolled if the informed consent is not withdrawn prior to participating in any study activity after screening. Potential participants who are screened for the purpose of determining eligibility for the study, but do not participate in the study, are not considered enrolled, unless otherwise specified by the protocol.

Participants will remain in the study for up to 13 weeks, including the screening and follow-up periods. Participants will be screened within 28 days of the first dose of IP and if all entry criteria are fulfilled, the participants will report to the CRU on the day prior to Day 1 dosing (Day -1) of each period. For Treatments A and B, following an overnight fast of at least 10 hours, on Day 1 of each period, participants will receive a high-fat and high-calorie breakfast prior to dosing which will need to be completely consumed within 20 minutes. For Treatment C, participants will be dosed after an overnight fast of at least 10 hours. Bosutinib will be administered as intact capsules with approximately 240 mL of ambient temperature water. Intact capsules will be swallowed and not chewed.

Tolerability and safety will be assessed for all treatments by monitoring AEs, ECGs, BP, pulse rate and safety laboratory data.

If there are participants who withdraw or discontinue treatment and are considered to be non-evaluable with respect to the primary PK objective, additional participants can be enrolled at the discretion of the investigator upon consultation with the sponsor.

Table 1. Study Schematics

Sequence	Period 1	Washout	Period 2	Washout	Period 3
1 (7 participants)	A	At least 14 days between successive bosutinib doses	B	At least 14 days between successive bosutinib doses	C
2 (7 participants)	B		A		C
3 (7 participants)	A		B		N/A
4 (7 participants)	B		A		N/A

Treatment A: 1 × 100 mg capsule under fed condition.

Treatment B: 4 × 25 mg capsules under fed condition.

Treatment C: 1 × 100 mg capsule under fasted condition.

2.2. Study Objectives

- **Primary Objectives:**
 - *To estimate the bioavailability of a single 100 mg capsule relative to four 25 mg capsules of bosutinib under fed condition in adult healthy participants.*
 - *To estimate the effect of a high-fat, high-calorie meal on the bioavailability of a single 100 mg capsule of bosutinib relative to fasted condition in adult healthy participants.*
- **Secondary Objectives:**
 - *To evaluate the plasma PK of bosutinib when administered as capsule formulation to healthy participants under fasted and fed conditions.*
 - *To evaluate the safety and tolerability of bosutinib when administered as capsule formulation to healthy participants under fasted and fed conditions.*

3. INTERIM ANALYSES, FINAL ANALYSES AND UNBLINDING

No interim analysis is planned. As this is an open-label study, the sponsor may conduct unblinded reviews of the data during the course of the study for the purpose of safety assessment. Final analysis will follow the official database release. As this will be an open-label study, there is no formal unblinding of the randomization code.

4. HYPOTHESES AND DECISION RULES

4.1. Statistical Hypotheses

No hypotheses are required.

4.2. Statistical Decision Rules

No decision rules are required.

5. ANALYSIS SETS

5.1. Pharmacokinetic (PK) Analysis Set

5.1.1. Concentration Analysis Set

The PK concentration population is defined as all subjects randomized and treated who have at least 1 concentration in at least 1 treatment period.

5.1.2. Parameter Analysis Set

The PK parameter analysis population is defined as all subjects randomized and treated who have at least 1 of the PK parameters of primary interest in at least 1 treatment period.

5.2. Pharmacodynamic Analysis Set

None.

5.3. Safety Analysis Set

All participants randomly assigned to study intervention and who take at least 1 dose of study intervention. Participants will be analyzed according to the product they actually received.

5.4. Other Analysis Sets

None.

5.5. Treatment Misallocations

All analyses will be performed on an “as-treated” basis and will not include data from subjects who are randomized but not treated.

If a subject takes a treatment that is not consistent with the treatment they are randomized to, for example takes a treatment out of sequence or takes the same treatment twice, then they will be reported under the treatment that they actually receive for all safety and PK analyses where applicable.

5.6. Protocol Deviations

Subjects who experience events that may affect their PK profile (eg lack of compliance with dosing) may be excluded from the PK analysis. At the discretion of the pharmacokineticist a concentration value may also be excluded if the deviation in sampling time is of sufficient concern or if the concentration is anomalous for any other reason.

A full list of protocol deviations will be compiled and reviewed to identify major and minor deviations prior to database closure.

5.6.1. Deviations Assessed Prior to Randomization

At Screening, the investigator will assess subjects against the inclusion and exclusion criteria as set out in Sections 5.1 and 5.2 of the protocol.

5.6.2. Deviations Assessed Post-Randomization

A full list of protocol deviations for the study report will be compiled prior to database closure. Any significant deviation from the protocol will be reviewed prior to database closure and a decision taken regarding evaluation for each analysis population.

6. ENDPOINTS AND COVARIATES

6.1. Efficacy Endpoint(s)

None.

6.2. Safety Endpoints

An adverse event will be considered a Treatment-Emergent Adverse Event (TEAE) if the event started during the effective duration of treatment. All events that start on or after the first dosing day and time/ start time, if collected, but before the last dose plus the lag time (28 days) will be flagged as TEAEs. The algorithm will not consider any events that started prior to the first dose date. Any events occurring following start of treatment or increasing in severity will be counted as treatment emergent.

Events that occur in a non-treatment period (for example, Washout or Follow-up) will be counted as treatment emergent and attributed to the previous treatment taken.

The following data are considered in standard safety summaries (see protocol for collection days and list of parameters):

- *adverse events,*
- *laboratory data.*

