8.3.1. Time Period and Frequency for Collecting AE and SAE Information

The time period for actively eliciting and collecting AEs and SAEs (“active collection period”) for each participant begins from the time the participant provides informed consent, which is obtained before the participant’s participation in the study (ie, before undergoing any study-related procedure and/or receiving study intervention), through and including a minimum of 28 calendar days after the last administration of the study intervention.

Follow-up by the investigator continues throughout and after the active collection period and until the AE or SAE or its sequelae resolve or stabilize at a level acceptable to the investigator.

For participants who are screen failures, the active collection period ends when screen failure status is determined.

If the participant withdraws from the study and also withdraws consent for the collection of future information, the active collection period ends when consent is withdrawn.

If a participant permanently discontinues or temporarily discontinues study because of an AE or SAE, the AE or SAE must be recorded on the CRF and the SAE reported using the CT SAE Report Form.

Investigators are not obligated to actively seek information on AEs or SAEs after the participant has concluded study participation. However, if the investigator learns of any SAE, including a death, at any time after a participant has completed the study, and he/she considers the event to be reasonably related to the study intervention, the investigator must promptly report the SAE to Pfizer using the CT SAE Report Form.

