10.3.1. Definition of AE

AE Definition

• An AE is any untoward medical occurrence in a patient or clinical study participant, temporally associated with the use of study intervention, whether or not considered related to the study intervention.• Note: An AE can therefore be any unfavorable and unintended sign (including an abnormal laboratory finding), symptom, or disease (new or exacerbated) temporally associated with the use of study intervention.

Events Meeting the AE Definition

• Any abnormal laboratory test results (hematology, clinical chemistry, or urinalysis) or other safety assessments (eg, ECG, radiological scans, vital sign measurements), including those that worsen from baseline, considered clinically significant in the medical and scientific judgment of the investigator. Any abnormal laboratory test results that meet any of the conditions below must be recorded as an AE:
• Is associated with accompanying symptoms;• Requires additional diagnostic testing or medical/surgical intervention;• Leads to a change in study dosing (outside of any protocol-specified dose adjustments) or discontinuation from the study, significant additional concomitant drug treatment, or other therapy.• Exacerbation of a chronic or intermittent preexisting condition, including either an increase in frequency and/or intensity of the condition.• New condition detected or diagnosed after study intervention administration, even though it may have been present before the start of the study.• Signs, symptoms, or the clinical sequelae of a suspected drug-drug interaction.• Signs, symptoms, or the clinical sequelae of a suspected overdose of either study intervention or a concomitant medication. Overdose per se will not be reported as an AE or SAE unless it is an intentional overdose taken with possible suicidal/self-harming intent. Such overdoses should be reported regardless of sequelae.

Events NOT Meeting the AE Definition

- Any clinically significant abnormal laboratory findings or other abnormal safety assessments that are associated with the underlying disease, unless judged by the investigator to be more severe than expected for the participant's condition.
- The disease/disorder being studied or expected progression, signs, or symptoms of the disease/disorder being studied, unless more severe than expected for the participant's condition.

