8.3.4. Adverse Events

Adverse events will be reported in accordance with the sponsor reporting standards by treatment.

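### SAP 6.2 gives conflicting instructions for an adverse event that starts before the first dose and worsens after it

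*SAP*

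**What the plan says.** SAP 6.2 (Safety Endpoints) contains four relevant rules.

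- **Onset.** An event is treatment emergent if it started during the effective duration of treatment. The window is: "All events that start on or after the first dosing day and time/ start time, if collected, but before the last dose plus the lag". That lag is set at 28 days.
- **Exclusion.** "The algorithm will not consider any events that started prior to the first dose date".
- **Severity.** The sentence that follows directly: "Any events occurring following start of treatment or increasing in severity will be counted as treatment emergent".
- **Attribution.** Events that occur in a non-treatment period, such as washout or follow-up, "will be counted as treatment emergent and attributed to the previous treatment taken".

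SAP 8.3.4 sets the reporting: "Adverse events will be reported in accordance with the sponsor reporting standards by treatment". Those standards are not reproduced in the SAP.

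Two protocol sections bear on this. Under Protocol 8.3.1 the collection period "begins from the time the participant provides informed consent". Protocol 10.3.1 lists among the events that meet the AE definition: "Exacerbation of a chronic or intermittent preexisting condition, including either an increase in frequency and/or intensity of the condition".

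**The concern.** The exclusion has no exception for worsening, and the severity sentence has no limit on onset. They collide for one class of event: onset before the first dose, increase in severity after it. Two programmers following SAP 6.2 in good faith could flag such an event differently.

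The class is not empty by construction. Collection starts at consent, and SAP 2.1 says: "Participants will be screened within 28 days of the first dose of IP". Events with onset up to about four weeks before dosing can therefore be on the CRF.

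AE monitoring is a secondary endpoint, and safety under fasted and fed conditions is a secondary objective (Protocol 3). A worsening after dosing is the part of such an event that could be related to the drug. If the onset definition and the exclusion are programmed as written, that worsening does not reach the TEAE tables by treatment. If the rule is left open until the events have been seen, the choice between readings is made with knowledge of the data.

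**Working it through.** The plan states no figure on this point, so there is nothing to reproduce. The check applies each rule to hypothetical event histories and then sizes one reclassification.

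**1. The rules applied to four histories**

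Assumptions: sequence A-B-C, with doses on study Days 1, 15 and 29 (the minimum 14-day washout). Days run continuously from the first dose, and worsening is placed by its date.

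| History | Onset definition and exclusion | Severity sentence |
|---|---|---|
| Onset Day -5, worsens Day 2 | Not treatment emergent | Treatment emergent, under A |
| Onset Day -5, worsens Day 16 | Not treatment emergent | Treatment emergent, under B |
| Onset Day 3 (after A), worsens Day 16 (after B) | Treatment emergent, under A | Treatment emergent, under A, and also under B if worsening is counted where it occurs |
| Onset Day 10 (washout after A) | Treatment emergent, under A | Treatment emergent, under A |

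The first two rows are the contradiction: the flag itself changes with the sentence followed. In the third row the event is flagged either way. Only its placement is open, because SAP 6.2 says nothing about it. The fourth row is settled by the attribution rule.

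**2. Whether the severity clause has another job**

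An event that starts after the first dose and within the window is already flagged by onset. For such an event the severity clause adds nothing to the flag. It changes the flag only for events with earlier onset, which the preceding sentence excludes.

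**3. Weight of one participant**

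Denominators come from the design table in SAP 2.1, with 7 participants per sequence.

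- A and B are each given in all 4 sequences: 4 × 7 = 28.
- C is given in 2 sequences: 2 × 7 = 14.
- One participant reclassified in A or B: 100 × 1/28 = 3.6 percentage points.
- One participant reclassified in C: 100 × 1/14 = 7.1 percentage points.

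These are simply 1/n. They show what one event is worth, not how many events to expect; the documents give no basis for that number.

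**The case against.** **A harmonising reading.** The severity clause could be meant only for events that start after the first dose. That removes the conflict, but it leaves the clause without effect on the flag, and the SAP does not say it.

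**Worsening as a new event.** Protocol 10.3.1 makes exacerbation of a pre-existing condition an AE, and Protocol 10.3.3 asks for one intensity category per AE. If the site enters a worsening as a new record with its own onset date, the onset rule captures it and places it under the later treatment. This is the strongest objection. It stands as a possibility, because neither document states the convention. The omission is therefore conditional: it occurs if worsening stays within the original record and the exclusion is programmed.

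**Sponsor standards.** SAP 8.3.4 defers to standards that may settle attribution. They cannot be checked here, and they would not remove two conflicting sentences from SAP 6.2.

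**Small practical effect.** Participants are screened healthy volunteers receiving single 100 mg doses, and few pre-dose events are likely to be ongoing and then worsen. There are no hypotheses or decision rules (SAP 4.1 and 4.2). Nor do the data vanish: all AEs are recorded on the CRF (Protocol 8.3.1.2), so only the flag and the tables built on it are in question. All of this stands and limits the weight of the point.

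**Conclusion.** SAP 6.2 contradicts itself for AEs that start before the first dose and increase in severity after it. The onset-only opening definition sides with the exclusion, so literal programming omits the worsening from the TEAE tables. The consequence is minor: probably few events, descriptive summaries, primary PK analysis unaffected. One reclassified participant is worth 3.6 points in A or B and 7.1 points in C. The conclusion assumes that a worsening is not already entered as a separate AE.

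Two stronger readings are not supported.

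- A reader might infer that the SAP never re-attributes worsening to a later treatment. The SAP is silent on an event that starts under one treatment and worsens under the next. Silence is not a rule, and the sponsor standards or the CRF convention may cover it.
- A reader might infer that Treatment C loses most, because it is always the last dose. The contradiction concerns onset before the first dose of the study, and Period 1 is always A or B. A pre-dose event would have to persist through both washouts, at least 2 × 14 = 28 days, and then worsen before C was involved. The 7.1 points reflect only the smaller denominator.

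**What to change.** Amend the opening definition and the exclusion sentence together, before database release. Changing only one would leave the conflict in place. The text would read:

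> An event is treatment emergent if it starts on or after the first dosing day and time, or started earlier and increases in severity after the first dose, and the onset or increase occurs before the last dose plus 28 days. An increase in severity after a dose is recorded as a new AE with its own onset date and is attributed to the most recent treatment taken before that date; the original event, if treatment emergent, stays with the treatment preceding its onset.

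This also settles the third history in the table: the original event stays under A and the worsening is counted under B.

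The cost is a short SAP edit and a small change to the AE programming. The downside is a dependency: the CRF completion instructions must confirm that worsening is entered as a new record, because the documents do not say that the date of a severity change is otherwise collected.

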Secondary: 
• To evaluate the plasma PK of bosutinib when administered as capsule formulation to healthy participants under fasted and fed conditions.• To evaluate the safety and tolerability of bosutinib when administered as capsule formulation to healthy participants under fasted and fed conditions.	Secondary: 
• Plasma AUC_{last}, T_{max}, CL/F, V_z/F and t_{1/2} for bosutinib.• Safety laboratory tests and AE monitoring.

Overall Design

This will be a Phase 1, randomized, open-label, 3-period, 4-sequence, crossover, single-dose study in healthy participants.

Number of Participants

Approximately 28 participants (7 participants per sequence) will be enrolled to study intervention. If there are participants who withdraw or discontinue treatment and are considered to be non-evaluable with respect to the primary PK objective, additional participants can be enrolled at the discretion of the investigator upon consultation with the sponsor.

Note: “Enrolled” means a participant’s agreement to participate in a clinical study following completion of the informed consent process and screening. A participant will be considered enrolled if the informed consent is not withdrawn prior to participating in any study activity after screening. Potential participants who are screened for the purpose of determining eligibility for the study, but do not participate in the study, are not considered enrolled, unless otherwise specified by the protocol.

Intervention Groups and Duration

Treatment Sequence	Period 1	Washout	Period 2	Washout	Period 3
1 (n=7)	A	At least 14 days between successive bosutinib doses	B	At least 14 days between successive bosutinib doses	C
2 (n=7)	B		A		C
3 (n=7)	A		B		N/A
4 (n=7)	B		A		N/A

Treatment A: 1 × 100 mg capsule under fed condition.

Treatment B: 4 × 25 mg capsules under fed condition.

Treatment C: 1 × 100 mg capsule under fasted condition.

Since the mean plasma elimination $t_{1/2}$ of bosutinib is approximately 34 hours (range 18 to 55 hours), there will be a minimum 14-day washout period between successive bosutinib doses.

Blood samples for bosutinib PK analysis will be collected predose and at 1, 2, 3, 4, 6, 8, 12, 24, 36, 48, 60, 72, 96, and 144 hours post the bosutinib dose in each period.

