3. OBJECTIVES AND ENDPOINTS

Objectives	Endpoints
Primary: 
To estimate the bioavailability of a single 100 mg capsule relative to four 25 mg capsules of bosutinib under fed condition in adult healthy participants.To estimate the effect of a high-fat, high-calorie meal on the bioavailability of a single 100 mg capsule of bosutinib relative to fasted condition in adult healthy participants.	Primary: 
Plasma AUC_{inf} and C_{max} for bosutinib. (AUC_{last} will be used as the primary estimate if AUC_{inf} cannot be reliably estimated).
Secondary: 
To evaluate the plasma PK of bosutinib when administered as capsule formulation to healthy participants under fasted and fed conditions.To evaluate the safety and tolerability of bosutinib when administered as capsule formulation to healthy participants under fasted and fed conditions.	Secondary: 
Plasma AUC_{last}, T_{max}, CL/F, V_z/F and t_{1/2} for bosutinib.Safety laboratory tests and AE monitoring.

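### The adverse-event attribution rule gives the fasted dose a longer window than the fed doses (28 versus 17.5 days on average at the minimum washout), which mildly tilts crude AE incidence by treatment against fasted dosing

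*SAP*

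**What the plan says.** SAP 6.2 (Safety Endpoints) sets two rules. Events starting on or after the first dose "but before the last dose plus the lag time (28 days) will be flagged as TEAEs". Events in a non-treatment period, with washout and follow-up given as examples, "will be counted as treatment emergent and attributed to the previous treatment taken".

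The 28-day limit matches the protocol's collection period, which runs "through and including a minimum of 28 calendar days after the last administration of the study intervention" (Protocol 8.3.1). On spacing, the synopsis says that "there will be a minimum 14-day washout period between successive bosutinib doses"; no maximum is given.

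The sequences in SAP 2.1 and Protocol 4.1 are ABC, BAC, AB and BA, with 7 participants each. The fasted arm ("Treatment C: 1 × 100 mg capsule under fasted condition") appears only in Period 3 of Sequences 1 and 2.

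On reporting, SAP 8.3.4 says: "Adverse events will be reported in accordance with the sponsor reporting standards by treatment". The secondary safety objective in Protocol 3 is "To evaluate the safety and tolerability of bosutinib when administered as capsule formulation to healthy participants under fasted and fed conditions". Neither document sets a common post-dose window, adjusts AE incidence for time at risk, or warns that the windows differ by treatment.

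**The concern.** In a crossover, assigning washout events to the preceding dose is usual, and it does no harm when every treatment is equally often last. Here C is last every time it is given, while A and B are each last in one sequence of four. The by-treatment AE table therefore counts events over unequal windows.

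Time since dosing makes the extra days mostly background. The protocol gives a mean half-life of about 34 hours (range 18 to 55), and 14 days is 336 hours, or 336/34 ≈ 10 mean half-lives and 336/55 ≈ 6 at the longest. Days 15 to 28 after C should add mainly events that the drug did not cause.

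What is at stake is the fed-versus-fasted reading of tolerability. AE and laboratory data are the safety results that the SAP summarises; vital signs and ECG are only held in the database (SAP 8.3.6, 8.3.7). Protocol 2.2.1 already expects food to improve tolerability, so a small artefact in that direction is unlikely to be questioned.

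**Working it through.** **Inputs.** Sequences and 7 per sequence: SAP 2.1. Lag of 28 days and attribution to the previous treatment: SAP 6.2. Interval between doses W ≥ 14 days: Protocol 1.1 and 4.1. Screening up to 28 days, follow-up at 28 to 35 days, and total time on study up to 13 weeks: Protocol 4.1.

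**Step 1: is 14 days the planned interval or only a floor?** Full screening, two 14-day intervals and the latest follow-up give 28 + 14 + 14 + 35 = 91 days = 13.0 weeks, which is the protocol's stated maximum. This supports 14 days as the plan but does not prove it: with follow-up at 28 days, an interval of 17.5 days also fits (28 + 2 × 17.5 + 28 = 91).

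**Step 2: window per dose.** A non-final dose has W days and a final dose has 28.

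| Treatment | Seq 1 (ABC) | Seq 2 (BAC) | Seq 3 (AB) | Seq 4 (BA) | Mean at W = 14 |
|---|---|---|---|---|---|
| A | W | W | W | 28 | (14+14+14+28)/4 = 17.5 days |
| B | W | W | 28 | W | (14+14+28+14)/4 = 17.5 days |
| C | 28 | 28 | – | – | 28 days |

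In participant-days this is 490 over 28 doses for A, the same for B, and 392 over 14 doses for C. The ratio of C to A or B is 28/17.5 = 1.6. Within Sequences 1 and 2, the only participants who receive both conditions, it is 28/14 = 2.0.

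**Step 3: sensitivity to the interval.** The mean for A or B is (3W + 28)/4.

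| W (days) | Mean A or B (days) | Ratio |
|---|---|---|
| 14 | 17.5 | 1.60 |
| 16 | 19.0 | 1.47 |
| 17.5 | 20.1 | 1.39 |
| 21 | 22.75 | 1.23 |
| 28 | 28 | 1.00 |

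Dropout also narrows the gap, because an early leaver's last fed dose keeps 28 days. With an assumed 5% to 10% leaving after each period, A averages about 17.9 to 18.4 days at W = 14.

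**Step 4: what this could do to the table.** The documents give no background AE rate, so the rates below are assumptions. With a constant rate r per day, no treatment effect and W = 14, the expected share of participants with at least one event is 1 − exp(−28r) on C and [3(1 − exp(−14r)) + (1 − exp(−28r))]/4 on A or B.

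| r per day | A or B | C | Excess (points) | Excess × 14 participants |
|---|---|---|---|---|
| 0.5% | 8.3% | 13.1% | 4.7 | 0.7 |
| 1% | 15.9% | 24.4% | 8.5 | 1.2 |
| 2% | 29.0% | 42.9% | 13.8 | 1.9 |

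The binomial standard error of the C proportion, √(p(1 − p)/14), is about 9.0, 11.5 and 13.2 points in the three rows. The artefact is at or below about one standard error.

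**Step 5: after the change.** Counting only events that start within 14 days of each dose gives A, B and C 14 days each, a ratio of 1.0.

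**The case against.** The case for leaving the plan alone has real force.

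- **Ascertainment is not constant over the window.** By the Schedule of Activities, every dose is followed by confinement to at least Day 4 and by contact on Days 5 and 7. A non-final dose then has one more scheduled contact, admission for the next period (about day 13). A C dose also has one more, a follow-up at 28 to 35 days that may be by telephone. Days 8 to 28 after C thus rest mainly on recall at a single contact, and a constant-rate model probably overstates the excess. This stands, and it is why the figures in Step 4 are best read as upper-end.
- **Nothing is decided on this comparison.** The SAP has no hypotheses and no decision rules, and the objective is to evaluate tolerability, not to test a contrast. This stands and lowers the severity.
- **There are partial safeguards.** The investigator assesses causality for every event (Protocol Appendix 3), so events judged unrelated can be identified. The sponsor reporting standards cited in SAP 8.3.4 are not available here and might include an adjustment. That cannot be excluded, but SAP 6.2 states its own attribution rule with no equalising step.
- **A common window does not make the comparison clean.** C is given only in Period 3, so it stays confounded with period. It would also be wrong to discard 28-day events that the protocol deliberately collects. Both points stand, and they argue for an added summary in place of a substitution.

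None of this removes the inequality of the windows, which follows from the rule and the sequences whenever doses are less than 28 days apart.

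**Conclusion.** The point holds as a minor one. The planned rule gives the fasted dose the longer window, by a factor of 1.6 at a 14-day interval with all participants completing, and of 2.0 within Sequences 1 and 2. The factor shrinks as the washout lengthens. The direction is against fasted dosing for crude all-causality incidence. The size in participants is unknown; about 1 to 2 of 14 is an illustration that depends on assumed constant rates.

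A reader might infer three stronger things that the documents do not support:

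- That the table will show a spurious excess of 5 to 14 percentage points. Those figures need a background rate that the documents do not give and uniform ascertainment that the visit schedule does not provide.
- That 17.5 days is a fixed property of the design. It is the value at the minimum washout with no dropout.
- That the trial's conclusions are compromised. The primary PK analysis does not use AE windows, A and B have equal windows, and no decision rule depends on the AE table.

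**What to change.** In SAP 6.2 and 8.3.4, keep the 28-day TEAE table as planned and add:

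1. A by-treatment AE summary limited to events that start within 14 days after each dose, applied alike to A, B and C. Any fed-versus-fasted tolerability statement should rest on this summary.
2. A footnote under the 28-day table saying that the attribution windows differ in length by treatment.
3. A sentence saying that C is given only in Period 3, so the fed-versus-fasted AE comparison remains confounded with period even with equal windows.

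The cost is one derived flag and one extra table. No event is lost, because the 28-day table stays. No primary endpoint or its analysis changes, so Protocol 9 does not call for an amendment.
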